## 2.4.2 Expected Number of Study Participants

Patients with stable CAD who have undergone ePCI coronary artery stenting without clinically significant procedural complications, require conventional antiplatelet therapy with a P2Y12 inhibitor, meet inclusion criteria, do not present exclusion criteria, and provide informed consent for participation will be selected and randomized for the study.

The sample size of 240 study participants is determined for inclusion in the study. Calculations were made using two instruments that provided two approximate sample sizes. The median of these values (considering that the greater level of significance of the odds ratio and the relative absolute risk values could be achieved with the larger sample size) was taken as the sample size.

(1) Calculate the sample size for scientific studies using a standard numerator based on the proportion of the population that is likely to have the demographic characteristics of the study sample and the size (number) of the population with the clinical characteristics expected for the study, with a 95% confidence level and a  $\pm 5\%$  confidence interval for the results of the statistical calculations.

(2) Sample size calculation for a randomized, parallel case-control study with a two-sided statistical significance level, at a confidence interval of  $\alpha = 0.05$ , at statistical power of  $(1-\beta) = 0.8$ , at case/control ratio of 2, at probability of occurrence of an event in the experimental arm of  $p_0$  – up to 0.4, and at probability of occurrence of an event in the control arm of  $p_1$  – up to 0.6.

Study participants will be randomly assigned to two parallel groups, control and experimental, with a 1:2 allocation ratio and selected 3 study arms for participants by CYP2C19 genotyping results:

1st arm – experimental: "Normal Metabolizers of Clopidogrel", 110 study participants diagnosed with chronic coronary artery disease who had undergone elective PCI, tested with CYP2C19 genotyping and identified as NFA \*2, \*3 carriers, who undergo CYP2C19 Genotype-Guided Clopidogrel Treatment - Clopidogrel as a component of preventive antiplatelet treatment such as double antiplatelet treatment (DAPT), or an antiplatelet drug (clopidogrel) combined with the non-vitamin K antagonist oral anticoagulants (NOAC), incl. triple antiplatelet treatment (Aspirin, Clopidogrel and a NOAC), or antiplatelet monotherapy (Clopidogrel).

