2nd arm - experimental: "Passive Metabolizers of Clopidogrel", approximately† 50 study participants diagnosed with chronic coronary artery disease who had undergone elective PCI, tested with CYP2C19 genotyping, identified as LOF \*2, \*3 allele carriers, who undergo CYP2C19 Genotype Guided Antiplatelet Treatment Alternative to Clopidogrel - an antiplatelet drug alternative to clopidogrel in conventional dosing regimen, as a component of preventive antiplatelet treatment, such as double antiplatelet treatment (DAPT) with ticagrelor or prasugrel, or prasugrel combined with the nonvitamin K antagonist oral anticoagulants (NOAC), or antiplatelet monotherapy (ticagrelor, or prasugrel).

3rd arm - active comparator: "Unspecified Metabolizers of Clopidogrel", 80 participants diagnosed with chronic coronary artery disease who had undergone elective PCI were allocated to the arm, without CYP2C19 genotyping through simple randomization, and having an unspecified metabolism phenotype, who were assigned to the conventional clopidogrel treatment - clopidogrel as a component of preventive antiplatelet treatment, such as double antiplatelet treatment (DAPT), or clopidogrel combined with the non-vitamin K antagonist oral anticoagulants (NOAC), incl. triple antiplatelet treatment (Aspirin, Clopidogrel and a NOAC), or antiplatelet monotherapy (Clopidogrel).

† The prevalence of carriers of CYP2C19 \*2, \*3 non-functional alleles in the Georgian population has not been studied and is unknown. To estimate the number of patients in subgroup II arm 1 and arm 2, we used the extrapolation of known data from a European population study [12].

2 study arms could be used as control for analyzing and comparing study outcome measures: 3rd study arm participants create the active comparators' group for 1st and 2nd arm, and besides, 2nd study arm participants - as the comparators for 1st arm:

Control 1: "Normal Metabolizers of Clopidogrel" - 110 study participants vs "Unspecified Metabolizers of Clopidogrel" - 80 participants;

Control 2: "Passive Metabolizers of Clopidogrel" - approximately 50 participants vs "Unspecified Metabolizers of Clopidogrel" - 80 participants;

Control 3: "Normal Metabolizers of Clopidogrel" - 110 study participants vs "Passive Metabolizers of Clopidogrel" - approximately 50 participants.

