## **2.6 Evaluation of Study Results**

### **2.6.1 Study Endpoints**

The study follow-up results will be discussed and presented by study arms, as well as concerning the primary and secondary endpoints of the study.

The study results will also be discussed concerning other endpoints, which will be represented by clinical or non-clinical data and characterize the factors that affect the efficacy of antiplatelet treatment and determine the clinical and non-clinical outcome in the course of the CCSs both with and without the results of CYP2C19 genotyping.

The indicators for assessing the effectiveness of the study are presented in Appendix 5.

In the study, the selection of treatment regimens with clopidogrel and an alternative P2Y12 inhibitor will be carried out by determining the genotype of the CYP2C19 \*2, \*3 non-functional alleles. Clopidogrel will be used in study participants with CYP2C19 \*2, \*3 normal allele genotypes and in the control arm of study participants not undergone CYP2C19 genotyping – unspecified CYP2C19 genotype. Study participants with CYP2C19 \*2, \*3 non-functional allele genotypes will be given alternative antiplatelet therapy.

In cases of CAD, regardless of treatment with P2Y12 inhibitors after ePCI, the clinical endpoints will be represented with MACCEs and other clinical conditions related to CAD or the potential adverse events of antiplatelet drug treatment. The incidence of the primary, secondary and other study endpoints defined as clinical outcomes of CYP2C19 genotype-guided P2Y12 inhibitor treatment will be assessed in the study arms.

The primary endpoints of the study are defined as:

- Number of study participants who died from any cause (Death from Any Cause) within a 12-month of the study follow-up;
- Number of study participants who died from any cardiovascular cause (Death from Cardiovascular Cause) within a 12-month of the study follow-up;

The secondary endpoints of the study are defined as:

- Number of study participants who experienced non-fatal myocardial infarction (Non-fatal Myocardial Infarction) within a 12-month of the study follow-up;
- Number of study participants who experienced unstable angina or angina requiring hospitalization (Unstable Angina) within a 12-month of the study follow-up;
- Number of study participants who experienced a stroke or transitory cerebral ischemic event (Stroke or TIA) within a 12-month of the study follow-up;

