## 2.6.2 Determining the Study Sample Size

The study sample size was determined at 240 patients.

In order to achieve representativeness of the sample, strength of evidence, high level of reliability and cost-effectiveness of the study, the minimum sample size calculations were performed using two tools that provided two approximate sample sizes. It is assumed that for the subsequent statistical analysis of the study results for calculating the odds ratio, relative risks and benefits, a larger number of variables would be better, and if the average of these two sizes of the study sample deviates towards the larger one, it was taken as the sample size.

The calculations were performed using the following tools:

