### **2.6.3 Statistical Analysis of Study Results**

Primary statistical analysis will be carried out using descriptive statistics methods. The values and distribution of quantitative and qualitative variables from the study participants' initial clinical assessment and follow-up results will be evaluated according to the experimental and control arms. The magnitudes and trends of the variations of the data values will be analyzed.

Quantitative variable data will be calculated by mean, standard deviation, and median. For comparative statistical analysis, differences between the variable values will be calculated using the t-test or the Wilcoxon signed-rank test.

Categorical variable data will be calculated as frequencies and percentages (%). For comparative statistical analysis, differences between the variable values will be calculated using the chi-square or Fisher's exact tests.

To analyze the effectiveness of selected study interventions, the frequency of detection of clinical endpoints in the experimental treatment intervention arms (Rt1 and Rt2) and the comparator arm (Rc) will be calculated. According to the frequencies of clinical endpoint-positive and -negative cases detected in the study arm, the odds ratio (OR), hazard ratio - Cox proportional hazards regression (HR), relative risk (RR), relative benefit (RB) and absolute benefit (AB) indicators at 95%CI will be calculated.

The obtained results and indicators of treatment intervention effectiveness will be selected to consider the applicability of the study findings and the possibility of the study results translation into real-world clinical practice.

Data evaluation will be carried out continuously, immediately after they enter the registration form and the database. Preliminary statistical calculations and analysis for study evaluation and monitoring will be provided in several stages, when:

I - More than 50% of patients will be included in the study;

II - The study arms will be fully formed, and more than 50% of patients will complete a 3-month and a 6-month follow-up;

III - All study participants will be included in the study, and at a minimum, half of them will complete a 6-month and a 12-month observation period;

IV - All study participants included in the study will complete a 12-month follow-up.

The development of clinical endpoints will be monitored, and the relevant data will be collected in a special data registration form.

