### 3.2 Adverse Event Reporting

#### 3.2.1 Definition of an Adverse Event

**Major Adverse Cardiovascular and Cerebrovascular Events (MACCEs):** A clinically significant adverse cardiovascular and cerebrovascular clinical event that occurs in CAD cases, which may be recurrent, incidental, with a frequency consistent with that expected in the course of the disease and the natural history of the disease (Hazard Ratio [HR], 1.26–5.68, 95%CI [4,5,7,18,23]), is quite common (1–10%) in terms of its probability, is severe in terms of its outcome, is associated with the impact of the risks associated with the disease even under optimal management, is clinically serious, may lead to death, may change the course of the disease/clinical condition, and is not preventable. MACCE determines the outcome of the clinical cases in the study and is, therefore, considered a study clinical endpoint. These include: Cardiovascular death, Nonfatal myocardial infarction, Recurrent angina, Stent thrombosis, Repeated PCI, CABG, Ischemic stroke, Transient ischemic attack, Intracerebral hemorrhage, Atrial fibrillation, Heart failure.

**Anticipated Adverse Medication Effect (AAME):** A serious adverse effect on the patient's health or a life-threatening problem or death associated with a medicinal product, in cases where the cause of the clinical effect, problem or death is already established and is consistent with previously studied possible effects of the medicinal product in its nature, severity or frequency of occurrence; an expected serious problem with the medicinal product that is related to the safety of the study participant. Possible adverse effects associated with treatment with clopidogrel, prasugrel, or ticagrelor are expected and are considered clinical outcomes and are considered clinical endpoints of the study: Bleeding requiring hospitalization, Thrombotic thrombocytopenic purpura, Minor or minimal bleeding, Change/discontinuation of P2Y12 inhibitor.

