	Denominator: the probability of developing death from any cause in the 'unspecified metabolizer' study participants' arm, calculated as the number of 'unspecified metabolizer' study participants dead from any cause divided by the sum of the number of 'unspecified metabolizer' study participants dead from any cause and number of 'unspecified metabolizer' study participants not dead from any cause;
The relative benefit (RB) of CYP2C19 *2, *3 genotype-guiding clopidogrel treatment application for avoiding death from any cause	Calculating: The relative benefit = 1 – the relative risk (RR) of developing death from any cause for 'normal metabolizer' study participants' arm vs 'unspecified metabolizer' study participants' arm
The relative benefit (RB) of CYP2C19 *2, *3 genotype-guiding any P2Y12 inhibitor antiplatelet treatment application for avoiding death from any cause	Calculating: The relative benefit = 1 – the relative risk (RR) of developing death from any cause for aggregated 'normal metabolizer' and 'passive metabolizer' study participants' arms vs 'unspecified metabolizer' study participants' arm
The absolute benefit (AB) of CYP2C19 *2, *3 genotype-guiding clopidogrel treatment application for avoiding death from any cause	Calculating: The absolute benefit (%) = the rate (%) of death from any cause among 'unspecified metabolizer' study participants – the rate (%) of death from any cause among 'normal metabolizer' study participants
The absolute benefit (AB) of CYP2C19 *2, *3 genotype-guiding any P2Y12 inhibitor antiplatelet treatment application for avoiding death from any cause	Calculating: The absolute benefit (%) = the rate (%) of death from any cause among 'unspecified metabolizer' study participants – the rate (%) of death from any cause among aggregated 'normal metabolizer' and 'passive metabolizer' study participants
The rate (percentage - %) of death from non-cardiovascular causes among study participants	Numerator: Number of study participants dead from non-cardiovascular causes Denominator: Total number of study participants
The rate (percentage - %) of death from non-cardiovascular causes among 'normal metabolizer' study participants	Numerator: Number of 'normal metabolizer' study participants dead from non-cardiovascular causes Denominator: Total number of 'normal metabolizer' study participants

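### The planned ratio measures for the two primary death endpoints become undefined, or read 100% benefit, when a group has no deaths, and the plan has no rule for that case

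*Combined protocol and SAP*

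**What the plan says.** Section 2.6.1 has two primary endpoints. The first is "Number of study participants who died from any cause (Death from Any Cause) within a 12-month of the study follow-up" and the second is death from a cardiovascular cause over the same period.

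On numbers, section 2.6.2 states "The study sample size was determined at 240 patients". Section 2.4.2 randomises control to experimental "with a 1:2 allocation ratio". It expects "80 participants diagnosed with chronic coronary artery disease" in the untested comparator arm, "110 study participants diagnosed with chronic coronary artery disease" in the normal-metabolizer arm, and about 50 in the passive-metabolizer arm.

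For analysis, section 2.6.3 lists chi-square or Fisher's exact tests for categorical data. It also says that OR, a Cox HR, RR, "relative benefit (RB) and absolute benefit (AB) indicators at 95%CI will be calculated". Appendix 3 gives the formulas for all-cause and cardiovascular death:

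- RB is one minus RR. For all-cause death the row reads "The relative benefit = 1 – the relative risk (RR) of developing death from any cause for aggregated" guided arms against the untested arm.
- HR is a ratio of crude proportions, despite its name.
- AB is the death rate in the untested arm minus the rate in the guided arm or arms.

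No section names an interval method, a continuity correction, a penalised model or a fallback for zero events, and the measures are not ranked. The Synopsis (primary statistical analysis) says that the effectiveness indicators to be used will be picked once results have been reviewed; section 2.6.3 reads similarly.

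No death rate is stated. The nearest figure, in section 3.2.1, is for the broad MACCE class, which "is quite common (1–10%) in terms of its probability".

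**The concern.** The plan has only 80 controls, and its primary outcome may be rare. A formula with the control death rate in the denominator gives no answer if no control dies. RB returns its maximum if no guided participant dies and one control does, however little that shows.

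Because the indicators are unranked and are chosen after the results are seen, a 100% relative benefit resting on one control death could become the reported finding. A rule for zero counts written after the zeros have appeared would carry little weight.

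**Working it through.** **Inputs.** Control n = 80. Guided n = 110 + about 50 = 160. Effect formulas are from Appendix 3. The death risk is an assumption, shown from 0.5% to 5%.

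**The plan's own event figures.** Section 2.6.2 uses event probabilities of up to 0.4 and up to 0.6, two-sided 0.05, power 0.8 and ratio 2, and obtains 221. The Kelsey formula reproduces this. The average probability is (2 × 0.4 + 0.6)/3 = 0.4667, and the control n is 7.849 × 0.4667 × 0.5333 × 1.5 / 0.2² = 73.26. Rounding up gives 74 + 147 = 221. At those probabilities about 0.6 × 80 = 48 control and 0.4 × 160 = 64 guided events would occur, and zero counts would not arise. But no endpoint is named for these probabilities, and they cannot plausibly be death rates beside 1–10% for MACCE.

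**What each measure does at zero**

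- No control deaths: RR, RB and the Appendix 3 HR have a zero denominator. The OR has no finite value.
- No guided deaths, at least one control death: RR and OR equal 0, so they are defined but uninformative, and RB = 1 − 0 = 100%. The Cox log-HR has no finite estimate and its Wald interval fails.
- AB is defined in every case.

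**How often.** With control risk p and guided risk p × RR:

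- P(ratio undefined) = (1 − p)^80
- P(RB = 100%) = (1 − p × RR)^160 × [1 − (1 − p)^80]

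| Assumed control risk | RR, RB, Appendix 3 HR undefined | RB = 100%, no effect | RB = 100%, true RR 0.5 |
|---|---|---|---|
| 0.5% | 67% | 15% | 22% |
| 1% | 45% | 11% | 25% |
| 2% | 20% | 3% | 16% |
| 3% | 9% | 0.7% | 8% |
| 5% | 2% | <0.1% | 2% |

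Example at 1%: 0.99^80 = 0.448; 0.99^160 × (1 − 0.448) = 0.200 × 0.552 = 0.11; 0.995^160 × 0.552 = 0.448 × 0.552 = 0.25.

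**Fewer observed participants.** Section 2.4.2 expects 75% to complete. With 60 controls observed, the undefined share is 0.99^60 = 55% at 1%, 30% at 2%, 16% at 3% and 5% at 5%. This is an upper case, because some who leave early still contribute data. Withdrawal after a registered MACCE (sections 3.2.6 and 3.3) may also leave later deaths unobserved.

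**What a 100% RB can rest on**

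- 0/160 v 1/80: Fisher p = 80/240 = 0.33. AB = 1.25%, Newcombe 95% CI −1.3% to 6.8%.
- 0/160 v 2/80: Fisher p = (80 × 79)/(240 × 239) = 0.11. AB = 2.5%, Newcombe 95% CI −0.5% to 8.7%.
- 0/160 v 0/80: RB does not exist. AB = 0, Newcombe 95% CI −2.3% to 4.6%.

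**Interval choice matters.** For 0/160 v 2/80 a Miettinen-Nurminen interval for AB is 0.1% to 8.7%. It excludes zero where Newcombe does not. The pooled score statistic shows why: 0.025 / √[(2/240)(238/240)(1/80 + 1/160)] = 2.01, or 2.00 after the √(239/240) correction, just above 1.96.

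**Exact upper limits for zero counts,** 1 − 0.025^(1/n): 4.5% for 0/80 and 2.3% for 0/160.

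**The case against.** A reader might infer that the primary effect cannot be estimated as specified. The documents do not support that. AB is specified for both death endpoints, arm-specific death rates are listed in Appendix 3, and Fisher's exact test is in section 2.6.3. All three survive zero counts. Only the ratio measures fail.

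A reader might also take it as given that deaths will be few. The plan states no death rate. The 1–10% in section 3.2.1 is for a MACCE list that includes cardiovascular but not non-cardiovascular death, so all-cause death is not a subset of it. Section 2.4.1 calls the risk lower only relative to patients after primary PCI or bypass surgery. Zero control deaths become more likely than not only below a risk of about 0.86% (0.9914^80 ≈ 0.5). The problem is common at about 1% or less, occasional at 2–3% and rare at 5%.

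Nor should the two failures be merged. An undefined ratio is the commoner one; a 100% RB under no effect is at most 15% over the range shown.

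It can fairly be said that the required 95% CI and Fisher's test would expose an empty 100%. A score interval for RR at 0/160 v 1/80 runs from 0 to 1.92, so RB runs from −92% to 100%. That helps only if such an interval is used, and none is named.

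The problem could be thought to extend to TTP, hemorrhagic stroke and CABG, which Appendix 3 treats the same way. The documents give no rates for them, so no claim is made here.

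**Conclusion.** The point holds for the ratio measures. For the two primary endpoints a written formula gives no value when no control dies and a misleading maximum when no guided participant dies, and the plan says nothing about either case. At an assumed equal death risk of 1% these occur in 45% and 11% of trials. At 2% they occur in 20% and 3%, and at 5% each is about 2% or less. If the true RR is 0.5, the second figure becomes 25%, 16% and 2%.

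The sizes rest on the assumed risk, the planned 160/80 split and full observation. Cardiovascular death cannot be more frequent than all-cause death, so it is affected at least as much. What makes this more than a missing detail is that the indicators are to be selected after the results are known.

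**What to change.** In section 2.6.3 and Appendix 3, before any results are reviewed:

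- For both death endpoints, name AB for the randomised comparison (both guided arms together against the untested arm) as the lead effect measure. Keep the Appendix 3 direction, conventional rate minus guided rate, so that benefit is positive.
- Give AB a 95% CI by Miettinen-Nurminen or Newcombe. Choose one now, since they can disagree at the counts shown above.
- Give exact upper limits for zero counts (0/80: 4.5%; 0/160: 2.3%).
- Report RR, OR and RB as not estimable when either group has no events.
- Estimate the HR by Cox regression as section 2.6.3 says, Firth-penalised if one group has no events and not estimable if neither has any. Delete the ratio-of-proportions HR in Appendix 3.
- Remove the choice of indicators after review of results for these endpoints.

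The cost is wording and standard software, with no change for participants. The small downside is that fewer ratio measures are reported. Treating RR = 0 as not estimable is a reporting convention; a score interval would be an alternative.

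The change makes the reporting valid but does not cure low power. Halving a 2% death risk has about 7% power by Fisher's test at 160/80, and 80% power would need about 4,977 patients.
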